5.0 Study Design and Statistical Analysis Plan

5.1 *Describe the basic study design/approach (e.g., qualitative study using five focus groups of first year students to describe assimilation into the university community; randomized controlled trial of a behavioral change intervention to increase dietary intake of whole grains; pre- post-test evaluation of new pedagogical techniques to improve adult literacy):*

This study is a randomized, cross-over intervention study that will evaluate the effect of brief, high-impact loading exercises on biomarkers of bone metabolism in energy-restricted, eumenorrheic female runners. Volunteers will complete two, 5-day experimental conditions in a randomized order separated by one menstrual cycle (approximately 3 weeks). Experimental conditions will include a dietary intervention of energy intake equal to 30 kcal/kgFFM/d using controlled diets and an exercise intervention of daily treadmill running with or without an additional 50 impact loading exercises.

5.2 Describe corresponding data analysis plan/approach (e.g., content analysis of focus group transcripts; descriptive analysis followed by linear regression modeling; nonparametric analysis of pre- and post-test measures):

Data will be analyzed using IBM SPSS statistics software. Paired t-test will be used to detect differences in bone biomarkers and hormones within and between experimental conditions (Aim 1). Associations between undercarboxylated osteocalcin concentration and glucose metabolism (i.e., interstitial glucose concentration and serum insulin) will be analyzed using regression analysis (Aim 2). Data will be summarized as mean \pm 1 standard deviation. The significance level will be set a priori at $p < 0.05$.

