4.0 Study Endpoints

4.1 *Describe the primary and secondary **study** endpoints. See links below for discussion of study endpoints and how they may differ from study objectives. These are most common in clinical trials but are sometimes applicable to other types of biomedical research, as well as social, behavioral, or educational research. See link below for a discussion.*

https://docs.google.com/document/d/1Wocz7K7a0hCQJPPO_khh5l1SQQjhGDDGHzcOPRHR5Tw/edit?usp=sharing

Primary Endpoints

Change in Biomarkers of Bone Remodeling in Blood including N-terminal propeptide of type 1 procollagen, undercarboxylated osteocalcin, sclerostin, and C-terminal telopeptide of type 1 collagen.

22-168 The Effect of Impact Loading on Bone Biomarkers in Energy-Restricted Female Runners

Change in Hormone and Metabolic Markers in Blood including parathyroid hormone, estrogen, insulin-like growth factor 1, hepcidin, insulin, cortisol, leptin, Nesfatin-1, and thyroid hormones

24-h Glucose

Secondary Endpoints

Change in Running Economy

Change in Body Weight

Change in ferritin, TIBC, iron, vitamin D

4.2 *Describe any primary or secondary safety endpoints. These should be included for all studies that are greater than minimal risk. (Minimal risk: The probability and magnitude of harm or discomfort anticipated in the research that are not greater in and of themselves than those ordinarily encountered in daily life or during the performance of routine physical or psychological examinations or tests.):*

Safety Endpoints

Excess weight loss (>5 lbs. during the 5-day experimental conditions)

Excessive change in absolute value for 24-hour glucose concentration

Excessive muscle soreness and/or pain

Fainting or light-headedness

Muscle or joint injury

General fatigue

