8.0 Procedures Involved

8.1 Describe and explain the study design:

This study will employ a cross-over design in which 12 eumenorrheic women between the ages of 18 and 35 will complete two experimental conditions in a randomized order using a computer program with a random number generator. The cross-over study design

22-168 The Effect of Impact Loading on Bone Biomarkers in Energy-Restricted Female Runners

will help control for inter-subject variability in response to LEA (Guebels, Kam et al. 2014, Reed, De Souza et al. 2015).

As outlined in the table, eligible participants will undergo two, 5-day experimental conditions separated by one menstrual cycle (approximately 24 days) consisting of an energy-restricted diet and endurance training regimen. Experimental conditions will include a dietary intervention of energy intake equal to 30 kcal/kgFFM/d using controlled diets and an exercise intervention of daily treadmill running with one condition of run only (RUN) and one condition with running and 50 high-intensity, impact loading “jumping” exercises (RUN+IL). After providing informed consent, participants will be randomly assigned to the RUN or RUN+IL condition. Outcome data will include assessment of serum biomarkers of bone metabolism and circulating hormones important for bone metabolism. Compliance to the nutrition and exercise regimen will be evaluated at regular intervals and include collection of packaging and uneaten food at the end of each 5-day condition, measurements of body weight before and after each experimental phase to assess change, and physical activity data collected by accelerometer and digital technology provided by the research team (Garmin smart watch and My PT Hub app).

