14.0 Number of Subjects

14.1 *Indicate the total number of subjects to be enrolled and how this number was determined (e.g., sample size calculation [show], number of available subjects in a finite pool, number of tests funding award would allow):*

A power analysis determined that 12 women will be required to detect a clinically significant change of 10 μ g/L in PINP with 80% power at $P < 0.05$ based on results from a similar study of LEA during dietary restriction (Papageorgiou, Martin et al. 2018). We aim to enroll 20 participants to account for possible dropout.

14.2 *If this is a multi-site study, indicate the number of subjects to be enrolled at this site and the total to be enrolled from all sites:*

N/A

14.3 *If applicable, indicate the number of potential subjects you expect to screen for enrollment, and the number of subjects you will need to complete the research procedures:*

We anticipate that we may need to screen between 50-60 participants to recruit and complete the required 12 participants.

14.4 If the study has more than one procedure, indicate the total number of subjects to undergo each procedure separately:

All enrolled participants will undergo the two experimental procedures.

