- *Describe any compensation to subjects. Separate compensation into appropriate categories, such as: reimbursement for expenses, time and effort, and additional incentives for study participation. For each category, specify the amount (including any pro-rated amount), schedule, and method of payment.*

A draft copy of our recruitment flyer is uploaded. This flyer will be posted at strategic locations throughout Blacksburg and the surrounding area. We will seek permission at each site as necessary before posting or hanging a flyer. We also plan to use this same advertisement for emails and a modified version for social media posts (that will be submitted for approval at a later date as an Addendum). Emails will use the subject line "Volunteers needed for study on bone health of long-distance runners". Participants will be compensated \$25 for completing the baseline visit and first experimental condition (7 days). Participants will be compensated an additional \$75 for completing the second experimental condition. This is a total of \$100 compensation for completing all testing visits and experimental conditions. Participants that do not complete the second condition will receive information about body composition, BMD, and aerobic fitness (VO2max, running economy), in addition to the \$25 compensation. Given the cross-over design of this study, data cannot be used for participants that do not complete both conditions. The experimental conditions will be separated by 3 weeks of their normal diet and exercise routine and not require any lab visits or intervention. The total time commitment for this study will be 19 days. Payment in the form of cash will be scheduled after each individual participant completes each experimental condition.

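### The between-condition paired t-test has no period term, and analysing only women who complete both conditions can leave the two sequences uneven

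*Combined protocol and SAP*

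**What the plan says.** Section 5.1 describes the design: "Volunteers will complete two, 5-day experimental conditions in a randomized order separated by one menstrual cycle (approximately 3 weeks". For the comparison of conditions, section 5.2 says only "Paired t-test will be used to detect differences in bone biomarkers and hormones within and between experimental conditions (Aim 1". Neither section 5 nor any other section mentions a period, sequence or carry-over term, a mixed model or a cross-over analysis of variance.

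On allocation, section 8.1 says the women "will complete two experimental conditions in a randomized order using a computer program with a random number generator". It gives no ratio, blocking or sequence balance; that wording fits a simple list or a blocked one.

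On who is analysed, section 15.4 says "Given the cross-over design of this study, data cannot be used for participants that do not complete both conditions". Section 14.1 says "A power analysis determined that 12 women will be required to detect a clinically significant change of 10" µg/L in P1NP, with 80% power, and then "We aim to enroll 20 participants to account for possible dropout". No rule replaces women who drop out in a way that would restore balance between sequences.

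The primary endpoint in section 4.1 begins "Change in Biomarkers of Bone Remodeling in Blood including N-terminal propeptide of type 1 procollagen". It is a change, and Table 1 places the blood draws on Day 1 and Day 7 of each condition. Section 5.2 does not say whether the between-condition test uses those changes or the Day 7 values.

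**The concern.** In a two-period cross-over, any systematic difference between period 1 and period 2 enters each woman's RUN+IL minus RUN difference. Its sign is positive if she did RUN+IL second and negative if she did it first. The paired t-test averages these differences without regard to sequence. If the sequences are equal in number, the period effect cancels from the mean but remains in the standard deviation. If they are unequal, part of it stays in the estimate and cannot be told apart from an effect of impact loading.

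Period 2 is each woman's second 5-day exposure to the same restriction and treadmill protocol, so a different response on repeat exposure is conceivable. If changes from each period's Day 1 are compared, only a period effect on the 5-day change matters, and a shift in level such as season cancels. If Day 7 values are compared, level shifts matter as well.

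Uneven completion is also conceivable. The plan tolerates losing 8 of 20 women. In section 8.2 the RUN+IL days need a morning session and a return 4 to 6 hours later, so dropout could depend on sequence. At stake is the P1NP comparison on which the sample size rests.

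**Working it through.** **Inputs from the documents.** 12 women required, 10 µg/L in P1NP, 80% power, P < 0.05 (section 14.1); 20 enrolled (section 14.1); completers of both conditions only (section 15.4); paired t-test (section 5.2).

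**Inputs not in the documents.** The SD of the paired difference, the sidedness of the test, the dropout rate and the size of any period effect. Period effects of 0 to 10 µg/L are assumed.

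**1. The plan's own figure.** Without an SD, N = 12 can only be back-solved. Taking 10 µg/L as the between-condition difference, with the noncentral t on 11 df and a two-sided 5% test, 80% power implies an SD of 11.25 µg/L. Other readings give 12.36 (two-sided normal), 13.05 (one-sided t) and 13.93 (one-sided normal). The work below uses 11.25. A larger SD makes a given period effect relatively smaller: 5/11.25 = 0.44 SD, against 5/13.93 = 0.36 SD.

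**2. Model.** D = τ + sπ + e. Here D is a woman's RUN+IL minus RUN difference, τ the condition effect, π the period effect, s = +1 if RUN+IL came second and −1 if first, and e has SD 11.25.

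**3. Shift of the paired estimate given the split.** It is π(n₁ − n₂)/N, where n₁ counts the women with RUN+IL second. This does not depend on the SD.
- 7:5: 2/12 = 1/6 of π
- 8:4: 4/12 = 1/3 of π, so 1.67 µg/L if π = 5
- 9:3: 6/12 = 1/2 of π, so 2.5 µg/L if π = 5

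**4. How often such splits occur with 12 completers.** These figures also do not depend on the SD.

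| Allocation | Not 6:6 | 8:4 or worse | 9:3 or worse |
|---|---|---|---|
| Balanced 10:10 list, 8 random dropouts (hypergeometric) | 65% | 17% | 2% |
| Simple randomisation (binomial) | 77% | 39% | 15% |

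**5. Even split: effect on the error term.** At 6:6 the expected sample variance of D is 11.25² + π² × 12/11. For π = 5 that is 126.6 + 27.3 = 153.9, so the standard error used is about √(153.9/12) = 3.58, although the true one is 11.25/√12 = 3.25. Simulated paired-test power to detect 10 µg/L:

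| π (µg/L) | 0 | 2.5 | 5 | 10 | With period term |
|---|---|---|---|---|---|
| 6:6 | 80% | 78% | 74% | 55% | 79% |
| 10:10 | 96.5% | 96.0% | 94.6% | 86.1% | 96.4% |

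**6. Type I error of the paired test at π = 5.** It is 3.3% at 6:6 (conservative), 5.4% at 8:4 and about 8.4% at 9:3. At 9:3 with π = 10 it is about 14%.

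**7. Period-adjusted analysis.** The estimate is half the difference between the two sequence means of the period 2 minus period 1 difference. SE = (SD/2)√(1/n₁ + 1/n₂), with N − 2 df. With SD/2 = 5.625:
- 6:6: SE 3.25, power 79%
- 7:5: SE 3.29, power 78%
- 8:4: SE 3.44, power 74%
- 9:3: SE 3.75, power 67%

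This power does not change with π, and the estimate is free of the shift in step 3. Averaged over simple randomisation it is 75%; averaged over a balanced list with random dropout to 12 it is 78%.

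**The case against.** The strongest reply is that the paired t-test is a valid choice. Averaged over simple randomisation its estimate is unbiased and its type I error is 5%. From a balanced list with random dropout to 12, average type I error is about 5.0%, 4.8% and 4% for period effects of 0, 2.5 and 5 µg/L, so it is slightly conservative. The 8.4% needs a 9:3 split, which such a list produces about 2% of the time.

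The period term also has a price. With no period effect it lowers power at every split. With 12 completers it breaks even only at a period effect of about 4 µg/L averaged over simple randomisation, about 3 from a balanced list, and about 2 at an exact 6:6. The documents show no period effect, and the design limits one: both conditions start on day 2 or 3 of menstruation, diets are standardised, exercise expenditure has the same target, and the endpoint is a change. Twelve completers of 20 means 40% dropout, and no dropout rate is stated. With 14 completers the paired test keeps about 80% power even at a period effect of 5 µg/L.

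All of this stands, and it limits the weight of the point. It does not remove it. Averaging over splits that did not occur is little comfort when one split will be observed and reported. The same design features that make a large period effect unlikely do not rule out a different response to a second exposure. If dropout depends on sequence, the imbalance is no longer random and the average no longer protects the estimate. Keeping the adjustment as a sensitivity analysis only would leave the choice between two answers open after the split is known.

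**Conclusion.** The concern holds, as an improvement that should be made and not as a fatal fault. The plan has no period term and no stated sequence balance, and its completers-only rule allows uneven sequences. Given the split, the shift is exactly (n₁ − n₂)/N of the period effect: nil at 6:6, one third at 8:4, one half at 9:3. At an even split the harm is lost power, from 80% to 74% for a period effect of 5 µg/L with 12 completers. With 20 completers at 10:10 the loss is small, 96.5% to 94.6%.

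The shift fractions and split frequencies follow from the counts, given random dropout for the frequencies. The power and error figures rest on the back-solved SD of 11.25 µg/L, on reading 10 µg/L as the between-condition difference with a two-sided test, and on assumed period effects; the documents supply none of these. Confidence in the practical size is therefore moderate.

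**What to change.** In section 5.2, replace the between-condition paired t-test with an analysis of change, defined as Day 7 minus Day 1 of the same period, that includes period. Either a linear mixed model with condition and period fixed and participant random, or the two-sample comparison of period differences between sequences, will do; with complete pairs they give the same estimate. Report the condition effect with a 95% confidence interval and the number of completers in each sequence.

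In section 8.1, state how the sequence list was generated. For any women not yet randomised, use permuted blocks over the two sequences.

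The text cost is one paragraph in 5.2 and one sentence in 8.1, settled before the data are analysed. The statistical cost is one degree of freedom plus some precision when the split is uneven. If there is in fact no period effect, 12 completers lose about 1 point of power at 6:6 (80% to 79%), 6 points at 8:4, 13 at 9:3, and about 5 averaged over simple randomisation. From a balanced list the average falls only to 78%, which is why balanced allocation should go with the period term. With 20 completers at 10:10 the cost is about 0.1 point. Twelve completers would then give slightly under the 80% stated in section 14.1, so that section should quote power for the period-adjusted analysis.

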2.0 Objectives

2.1 *Describe the purpose, specific aims, or objectives of this study:*

- 1) Determine the effect of short-term, high-impact loading on biomarkers of bone remodeling in energy-restricted, female long-distance runners.
- 2) Examine the relationship between undercarboxylated osteocalcin and impact loading on glucose metabolism during acute low energy availability.

2.2 *State the hypotheses to be tested:*

The addition of 50 high-intensity impact loading jumping exercises per day to usual run training will result in less suppression of bone formation following 5 days of endurance running in an energy-restricted condition compared to daily running in an energy-restricted state without high-impact loading exercises.

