serum N-terminal pro-peptide of type 1 collagen (P1NP), a marker of bone formation, and IGF-1 decreased by 15% and 17%, respectively, after 3 consecutive days of treadmill running with energy intake restricted to 50% of estimated needs (Zanker and Swaine 2000). In a more recent cross-over design study (Papageorgiou, Elliott-Sale et al. 2017), changes bone biomarkers were measured in 11 women and 11 men in response to 5 days of daily running under optimal EA conditions (45 kcal/kgFFM/d) and 5 days of daily running under low EA conditions (15 kcal/kgFFM/d). In both conditions, participants ran on a treadmill until an energy expenditure of 15 kcal/kgFFM was achieved. Diets provided 60 kcal/kgFFM/d and 30 kcal/kgFFM/d for the optimal and low EA conditions, respectively. In the female participants, P1NP was significantly lower after the low EA condition compared to optimal EA. Additionally, β -carboxyl-terminal cross-linked telopeptide of type 1 procollagen (β -CTX), a marker of bone resorption, increased 19% in response to the low EA condition and this increase was significantly different from the change in β -CTX observed in the optimal EA condition. No significant change in P1NP or β -CTX were observed in men. This suggests women may be more sensitive to the effects of LEA on bone metabolism and, therefore, be at greater risk. In another cross-over design study of 10 female runners, changes in P1NP and β -CTX were measured after completion of three, 3-day experimental conditions: optimal EA (45 kcal/kgFFM/d), LEA achieved through dietary restriction only (15 kcal/kgFFM/d), and LEA achieved through a combination of dietary restriction and daily running (15 kcal/kgFFM/d) (Papageorgiou, Martin et al. 2018). In the combined diet and exercise LEA condition, participants received diets providing 30 kcal/kgFFM/d and expended 15 kcal/kgFFM/d during a treadmill run. This study found P1NP was significantly reduced after 3 days of LEA achieved through diet only, but not after the combined LEA condition with running. These findings suggest the negative effects of LEA on bone metabolism may be counteracted or masked by the osteogenic effects of weight-bearing exercise, such as running. There were no significant changes observed in β -CTX in response to either LEA condition. Based on these short-term studies, it appears suppression of bone formation occurs before measurable increases in bone resorption. Additionally, the severity of bone impairments may depend on the degree of energy restriction given the dose-response relationship observed between LEA and select bone turnover markers in exercising women (Ihle and Loucks 2004).

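### Could a P1NP fall that is significant in RUN but not in RUN+IL be taken as the answer to the hypothesis in 2.2, because 5.2 does not rank its Aim 1 t-tests?

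*Combined protocol and SAP*

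**What the plan says.** Section 2.2 states one comparative hypothesis: adding 50 jumps a day "will result in less suppression of bone formation following 5 days of endurance running in an energy-restricted condition", relative to the same running and diet without jumps. Section 4.1 lists the bone markers, P1NP among them, as changes. Blood is taken on Day 1 and Day 7 of each condition (Table 1 and 8.3). Each woman therefore gives a RUN change, a RUN+IL change and the difference between the two.

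Section 5.2 is the whole analysis plan for Aim 1: "Paired t-test will be used to detect differences in bone biomarkers and hormones within and between experimental conditions (Aim 1"). One significance level, p<0.05, covers everything. No section ranks the tests or calls the within-condition ones descriptive.

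On size, 14.1 says: "A power analysis determined that 12 women will be required to detect a clinically significant change of" 10 µg/L in P1NP with 80% power, "based on results from a similar study of LEA during dietary restriction". It does not say whether that change lies within a condition or between conditions. It plans to enrol 20 to allow for dropout. Section 14.3 speaks of the number screened to "recruit and complete the required 12 participants", and 15.4 says that data from women who do not finish both conditions cannot be used.

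**The concern.** A within-condition test asks whether P1NP moved in that condition. It does not ask whether it moved less with jumps. If P1NP truly falls by the same amount in both conditions, sampling error can push one fall past p<0.05 and leave the other short of it. Reading that pattern as a jumping benefit is a familiar error, and 5.2 places the two kinds of test side by side.

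The Background adds to the worry. Section 3.1 describes the study later used for the sample size: "P1NP was significantly reduced after 3 days of LEA achieved through diet only, but not after the combined LEA condition with running". It then says: "These findings suggest the negative effects of LEA on bone metabolism may be counteracted or masked by the osteogenic effects of weight-bearing exercise". It also sets significant results in women against no significant change in men and remarks: "This suggests women may be more sensitive to the effects of LEA on bone metabolism and, therefore, be at greater risk". If the trial's own results were read this way, it could report a bone benefit that its between-condition test does not support. Section 14.1 does not settle the matter, because the study it draws on had, as 3.1 describes it, no jumping condition.

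**Working it through.** **1. The plan's own figure.** Section 14.1 gives n = 12, 80% power, 10 µg/L and P<0.05, but no SD, so 12 cannot be reproduced outright. It can be solved for the SD it implies. For a two-sided paired t-test with 11 degrees of freedom, noncentral-t power of 80% needs d = 0.889, so SD = 10 / 0.889 = 11.25 µg/L. With 20 women the matching d is 0.660.

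**2. Chance of the misleading pattern.** Assumptions, none given by the documents: no jumping effect, equal true falls, normal changes, two-sided 0.05, SD of 11.25 for each change, and correlation rho between a woman's two changes. The pattern is a significant fall in RUN and none in RUN+IL. When rho = 0 its probability is p(1 − p), where p is the power of one within-condition test. For n = 12 and a fall of 10, p = 0.80, so 0.80 × 0.20 = 0.16. The expression cannot exceed 0.25, which it reaches at p = 0.5. Simulation gives the other correlations:

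| Completers | True fall (µg/L) | rho 0 | 0.25 | 0.5 | 0.7 |
|---|---|---|---|---|---|
| 12 | 10 | 16% | 14% | 12% | 9% |
| 12 | 7.5 | 25% | 21% | 17% | 13% |
| 12 | 5 | 21% | 18% | 15% | 11% |
| 20 | 10 | 3% | 3% | 3% | 2% |
| 20 | 7.5 | 16% | 14% | 11% | 9% |
| 20 | 5 | 25% | 21% | 17% | 13% |

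The between-condition test favours jumping in about 2.5% of trials in every cell. In the 12-completer cells, about nine in ten trials that show the pattern have a between-condition test that does not favour jumping.

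**3. Sensitivity.** If 11.25 is instead the SD of the between-condition difference, the rates run from 2% to 25% with 12 completers and from 0.0% to 20% with 20. Falls of 5 to 10 lie around the peak of p(1 − p). Outside that range, with 12 completers and the SD reading of step 2, the pattern appears in about 3% to 5% of trials at a fall of 1 and about 1% at a fall of 15.

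**4. Which test answers 2.2.** The sections read together as follows:

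- 2.2: less suppression with jumps than without, which is a contrast between conditions.
- 4.1: the endpoint is a change.
- 5.2: a paired t-test between conditions is planned.
- 15.4: only women with both conditions are usable, as a paired contrast requires.

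These lead to the paired test of RUN+IL minus RUN in Day 1 to Day 7 P1NP change. A within-condition test can show whether suppression occurred in RUN, which the phrase about less suppression takes for granted.

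**5. What 14.1 can mean.** If 10 µg/L is a between-condition difference, the stated 80% at 12 applies to the right contrast. If it is a change within one condition with SD 11.25, the SD of the difference is 11.25 × √(2(1 − rho)). Power at 12 for a difference of 10 is then 51%, 63%, 80% and 95% at rho 0, 0.25, 0.5 and 0.7. At rho = 0.5 the two readings coincide, since √(2 × 0.5) = 1. The documents do not show 12 or 80% to be wrong.

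**The case for a change.** The best argument for an edit is that a plan should settle before the data which test governs. Section 5.2 gives both kinds of test the same standing and the same alpha, the Background shows a readiness to compare significance across conditions, and one sentence would close the gap at no cost in visits or participants. Nor does full enrolment remove the risk: with 20 completers and a fall of 5 µg/L, the pattern still appears in 13% to 25% of trials on the reading in step 2.

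Part of this stands. No section ranks the tests, the simulated rates reproduce, and 14.1 does not name its contrast.

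The rest is weaker. A significant fall in one condition, a non-significant fall in the other and a null difference do not contradict each other; only the last bears on 2.2. The Background evidence is also mixed. For the five-day study, 3.1 reports P1NP in women compared between the two energy conditions, and a CTX rise compared with the CTX change in the other condition. The second of these is exactly a difference-of-changes comparison. Hedged summaries of other groups' studies say little about how this team will analyse its own trial.

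**Conclusion.** The concern does not call for a change. The test that answers 2.2 is already in 5.2, and 2.2 and 4.1 identify it. Followed as written, it holds its error rate: about 2.5% in favour of jumping when there is no effect, under the normal model used here, which ignores period and sequence effects. The harm needs a further step that no section plans, namely reporting a significance contrast in place of that test.

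The figure of 9% to 25% shows how misleading that step would be with 12 completers. It does not measure a fault in the plan. It rests on an SD solved back from 14.1, on falls chosen near the worst case and on assumed correlations; other plausible inputs bring it down to 1% to 5%. The missing ranking sentence, and the unnamed contrast in 14.1, are details that an analyst can settle from 2.2 without altering any test, sample size or planned conclusion.

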22-168 The Effect of Impact Loading on Bone Biomarkers in Energy-Restricted Female Runners

body weight will be measured on a digital physician's scale. Participants will complete the LEA experimental trials on days 2-6. A follow-up blood sample will be collected on the morning of day 7 after an overnight fast and body weight will be measured on a digital physician's scale.

Pregnancy Test: a pregnancy test will be performed after the 3-week washout period on day 1 of the second experimental condition.

Blood Draw: Blood (approximately 20-25 ml) will be drawn the days before and after each LEA experimental trial by venipuncture after a 12-hr fast (no caffeine) for the following: Progesterone, total and free 25(OH)D, N-terminal propeptide of type 1 procollagen, undercarboxylated osteocalcin, sclerostin, C-terminal telopeptide of type 1 collagen, parathyroid hormone, estradiol, insulin-like growth factor, hepcidin, ferritin, TIBC, iron, cortisol, leptin, nesfatin-1, insulin, free T3, free T4, rT3. In total, blood will be drawn five times during the study by venipuncture from a vein in the arm with a total of 110 ml obtained for the duration of the study. Blood will be drawn with the participant seated quietly in a phlebotomy chair.

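### The between-condition paired t-test fixes the Day 1 slope in advance; adjusting for the Day 1 difference already collected would probably make the P1NP comparison more precise, at small cost

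*Combined protocol and SAP*

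**What the plan says.** Section 5.2 gives one method for Aim 1: "Paired t-test will be used to detect differences in bone biomarkers and hormones within and between experimental conditions (Aim 1". No covariate, ANCOVA or mixed model is named for this aim; regression is reserved for Aim 2. Section 5.2 does not say whether the between-condition test is applied to changes or to Day 7 values.

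Section 4.1 points to changes: "Change in Biomarkers of Bone Remodeling in Blood including N-terminal propeptide of type 1 procollagen".

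Table 1 and section 8.2 show that P1NP and most other markers are drawn on Day 1 and Day 7 of both conditions. Section 8.2 says of the second draw: "A follow-up blood sample will be collected on the morning of day 7 after an overnight fast". A Day 1 value will therefore exist for each woman in each period.

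Section 14.1 sizes the trial on P1NP: "12 women will be required to detect a clinically significant change of 10" µg/L, "with 80% power at" P < 0.05. It gives no SD and says only that the calculation is "based on results from a similar study of LEA during dietary restriction".

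**The concern.** The hypothesis in section 2.2 is a between-condition claim: less suppression of bone formation with jumping than without. In a cross-over, stable differences between women cancel when each woman's two conditions are compared. What remains in her Day 1 difference is fluctuation from one period to the other. Some of it carries through to Day 7 and some does not.

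A change score assumes that all of it carries through (slope 1). A Day 7-only test assumes that none does (slope 0). If the truth lies between, either test leaves removable noise in the estimate. A regression lets the data set the slope. With as few as 12 completers, precision is scarce, and the samples needed are already being paid for.

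**Working it through.** **1. The plan's own figure.** The 12 women in section 14.1 cannot be reproduced forwards, because no SD is given. They can only be back-solved. For a paired t-test with n = 12, a difference of 10 µg/L, two-sided 0.05 and 80% power, the noncentral t gives a standardised difference of 0.889, so SD = 10 / 0.889 = 11.25 µg/L. The normal approximation gives 10 × √12 / (1.960 + 0.842) = 12.36. A one-sided test would imply 13.05; the documents do not state sidedness.

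**2. Set-up.** For each woman let x be the RUN+IL minus RUN difference on Day 1, and y the same difference on Day 7. Assume that x and y have equal SD s and correlation rho. The variances of the three estimates are:

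- change score, mean of (y − x): 2s²(1 − rho)/n
- Day 7 only, mean of y: s²/n
- adjusted, intercept of y on x: [s²(1 − rho²)/n] × (n − 2)/(n − 3)

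The ratios are therefore:

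- adjusted to change score: [(1 + rho)/2] × (n − 2)/(n − 3)
- adjusted to Day 7 only: (1 − rho²) × (n − 2)/(n − 3)

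**3. Break-even points.** At n = 12 the last factor is 10/9 = 1.111. Adjustment beats the change score when (1 + rho)/2 < 0.9, that is rho < 0.80. It beats Day 7 only when rho² > 0.1, that is rho above about 0.32. At n = 20 the factor is 18/17 = 1.059, and the break-even points move to about 0.89 and 0.24.

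**4. Power at n = 12.** The SD of the difference in changes is set to 11.25, so the change-score test has 80% power. Powers are simulated.

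| rho (assumed) | variance, adjusted / change | change score | adjusted | Day 7 only |
|---|---|---|---|---|
| 0 | 0.556 | 80% | 96% | 98% |
| 0.3 | 0.722 | 80% | 90% | 91% |
| 0.5 | 0.833 | 80% | 86% | 80% |
| 0.7 | 0.944 | 80% | 82% | 58% |
| 0.8 | 1.000 | 80% | 80% | 43% |
| 0.9 | 1.056 | 80% | 77–78% | 24% |

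The simulated type I error is close to 5% for all three tests.

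**5. The other reading.** If the Day 7-only test is instead the one with 80% power at n = 12, the adjusted test has 76% (rho 0), 77% (0.2), 79% (0.3), 83% (0.4), 86% (0.5) and 91% (0.6).

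**6. If all 20 complete.** With the same SD the change score has about 96% power. Adjustment gives about 99% at rho 0.5 and 96% at rho 0.9. On the Day 7-only reading, the loss at rho 0 is about 1 point (96.5% to 95.4%).

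**7. Chance Day 1 imbalance.** At rho 0.5, s = 11.25 / √(2 × 0.5) = 11.25, so the standard error of the mean Day 1 difference at n = 12 is 11.25/√12 = 3.25 µg/L. An imbalance of that size shifts the change-score estimate by (0.5 − 1) × 3.25 = −1.6 µg/L and the Day 7-only estimate by 0.5 × 3.25 = +1.6 µg/L, against a target of 10. The squared shift is a share (1.62/3.25)² = 0.25 of the change-score variance. That is the large-sample saving, 1 − (1 + 0.5)/2 = 0.25. The imbalance and the lost precision are one quantity seen twice.

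**The case against.** The strongest reply is that a paired t-test on change is a standard, valid cross-over analysis that already uses Day 1, so covariate adjustment is only an efficiency preference whose benefit rests on an unknown rho. Much of this stands.

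- A reader might infer that the plan ignores baseline. It does not: with section 4.1, Day 1 most naturally enters by subtraction. What is open to question is the fixed slope.
- A reader might infer that the planned estimate is biased. Order is randomised (sections 5.1 and 8.1), so either unadjusted estimate is unbiased over randomisation. The 1.6 µg/L shift is conditional on a chance imbalance and already lies inside the t-test's standard error.
- A reader might infer that the loss of precision is certain. It is not. At n = 12, adjustment beats both t-tests only for rho between about 0.32 and 0.80. Day 1 and Day 7 fall in the same week while the conditions are weeks apart, so shared period effects could make rho substantial.
- At low rho most of the gain over the change score comes from not subtracting Day 1; at rho 0 a plain Day 7 test does slightly better (98% against 96%).
- The implied SD assumes that section 14.1 concerns the between-condition change. Its wording could equally mean a change within one condition.

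What survives is the asymmetry. With rho unknown, the adjusted test loses at most about 3 points against the change score over the range shown, and gains up to about 16. Against Day 7 only it loses at most 4 to 5 points, and gains 6 at rho 0.5 and 11 at rho 0.6. Neither fixed slope is protected in this way: the Day 7-only test falls to 24% at rho 0.9.

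**Conclusion.** The point holds as a likely and cheap gain in precision, not as an error that invalidates the analysis. Section 5.2 uses an unadjusted paired t-test, does not name its outcome, and on either reading fixes a slope that the collected data could estimate. At n = 12, relative to a change-score test with 80% power, adjustment gives between about 96% (rho 0) and 77–78% (rho 0.9), with 86% at rho 0.5.

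These figures rest on four assumptions: section 14.1 powers the between-condition change score; the test is two-sided; the Day 1 and Day 7 differences have equal SD; and rho lies within the range shown. The documents do not settle rho, so the actual gain cannot be stated. It also matters less if completers approach 20. The documents do not support a claim of systematic bias, of an inflated type I error, or of an underpowered trial on this ground.

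**What to change.** In section 5.2, for every marker drawn on Day 1 and Day 7, pre-specify a regression of the within-woman Day 7 difference (RUN+IL minus RUN) on the within-woman Day 1 difference. Report the intercept, with a 95% confidence interval, as the treatment effect. Keep the paired t-test as a sensitivity analysis and state that it is on change. Naming the outcome and the adjustment in advance also prevents a choice among the three analyses after the data are seen.

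The cost is one added sentence and one degree of freedom, with no new samples or visits. At n = 12 the price is about 2 to 3 points of power against the change score if rho is about 0.9 (break-even about 0.8), and up to about 4 to 5 points against a Day 7-only test if rho is below about 0.3. Both losses are smaller at n = 20.
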